The study will be performed at the Baylor College of Medicine. Approval from Site Review Authority will be obtained. Subjects will be recruited from outpatient clinics at Baylor College of Medicine.

We propose a randomized crossover trial (Phase I/II) to evaluate acceptability as well as short (1 week) and intermediate (6 week) benefits and effectiveness of Orthofeet in reducing foot pain, increasing daily physical activities, and improving functional performance in ambulatory patients suffering from foot pain.

We are proposing a clinical study at the Baylor College of Medicine, to evaluate short and intermediate benefits and effectiveness of a novel pain relief footwear, called Orthofeet. This is a randomized crossed over trial. The duration of the study would be 12-week. We will recruit 50 eligible ambulatory adults (age 50 years or older) with moderate to severe self-reported foot pain. Participants will be randomly assigned to Group A (25 subjects) and Group B (25 subjects). There is no difference in assessments or eligibility between Group A and Group B, the only difference is when they have the opportunity to try the shoes for 6 weeks. Group A will receive a pair of Orthofeet shoes with adjustable insoles and will be asked to wear it every day activities of daily living for duration of six weeks. Participants will be also encouraged to wear the shoes inside of home if possible. Group B will be followed for duration of six weeks. At six weeks the groups will be switched and group B will receive a pair of Orthofeet shoes with adjustable insoles and Group B will follow-up for six weeks without Orthofeet shoes. Participants will be assessed at baseline, week-1, week-6, week 7, and week 12.

The primary outcome includes changes compared to baseline in foot pain intensity.

The secondary outcomes includes changes compared to baseline in various metrics of daily physical activities (e.g., daily step, longest walking bout, cadence, standing duration, and standing duration).

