Exclusion criteria: Patients with plantar ulcer Patients with major foot deformity (e.g., Charcot foot, Pes Cavus) Patients with lower extremity amputation including minor amputation. Foot pain because of nail disorder or keratotic lesions (e.g. corns, calluses) Patients with unstable conditions (e.g., recent stroke, anticipated changes in medication regime) Acute fractures of the foot Participation in an interventional Study such as exercise intervention within the last 30 days Non-ambulatory or unable to stand without help or walk a distance of at least 6 feet without assistance. Patients with major cognitive impairment or major depression Patients who are unable or unwilling to participate in all procedures and follow up evaluations

F2. Procedure

7) The research will be conducted at the following location(s): Baylor College of Medicine and Baylor St. Luke's Medical Center (BSLMC). Duration of study: 12 weeks

Research staff may contact you for any study related questions throughout your participation in the study

Visit 1 (Baseline): Maximum duration 120 minutes

Screening: Measurements will take place at your home, or in Baylor Clinic based on your preference. Participants will be randomly placed in either Group A or Group B. Group A wears the OrthoFet shoes from baseline to 6 week follow up and Group B wears OrthoFet shoes from 6 week follow up to 12 week follow up.

All the same assessments and questionnaires are completed at each visit for all participants.

Foot Pain: Foot pain will be assessed by the revised Foot Function Index (FFI). FFI was developed in 1991 to measure the impact of foot pathology on function in terms of pain, disability, and activity restriction. It is a self-administered index consisting of 23 items divided into 3 sub-scales. Both total and sub-scale scores are produced. The FFI has been shown to be a reasonable tool for use with low functioning individuals with foot disorders, patients with rheumatoid arthritis, and non-traumatic foot or ankle problems. It can be used in both clinical and research settings. Foot pain will be assessed at baseline, week-1, week-6, week-7, and week-12.

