Patient acceptability: We will use a Technology Acceptance Model (TAM) survey adapted for footwear to determine perceived benefit, perceived ease of use, acceptability, and attitude toward daily use. Patient acceptability will be assessed at the end of week 6 active use of OrthoFet (6- week for Group A and 12 week for group B) or the conclusion of the study for early endpoint.

Ancillary Measurements Patient-reported outcomes: Self-reported pain level will be extracted from FACT-G; ADL will be assessed using Katz Index of Independence in ADL; Community engagement will be assessed using the Life-Space Assessment questionnaire; The Fall Efficacy Scale-International (FES-I) questionnaire to determine concern for falls. Anxiety will be assessed using the Beck Anxiety Inventory questionnaire; cognition will be assessed using Montreal Cognitive Assessment (MoCA). Patient-reported outcomes will be assessed at baseline, week 6 and week 12. The subjects will not be advised or counseled based on the results of the questionnaires, these tools are not diagnostic, but the coordinators will try to provide possible resources if asked by the subject.

Digital Photographs , may take digital photographs of the subjects while performing exercise or during assessments for the purpose of publication (conferences/manuscripts). **Physical frailty:** Frailty will be assessed by trauma-specific frailty index and a validated wearable frailty meter technology.

Health related questionnaires: A series of health related questionnaires will be used to evaluate your quality of life , fear of falling, fall history, mobility, activities of daily living, depression, frailty, mental exams, foot examinations, pain intensity levels. Your medical history (from your clinic chart such as: medication use, prior surgery, diagnosis, progress notes, etc.) and demographic information will be obtained, such as age, gender, weight, and height. These questionnaires are asked to review the subject holistically and assess changes in their overall health, including mental and physical, over the 3 month span. The relevance to foot pain is to see how these components of health are related to foot pain such as finding a connection between their foot pain and fear of falling doing different activities.

At Visit 2 (1 Week Follow Up) the participant is called by the research staff to complete the pain questionnaire, document adverse events, and answer any study-related questions.

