At Visit 3 (6 Week Follow Up) the participant will complete all the same assessments and questionnaires as baseline. At this visit, Group A will stop wearing OrthoFet shoes and continue the study without them. Group B will be supplied with OrthoFet shoes to wear for the rest of their study participation until 12 Week Follow Up.

At Visit 4 (7 Week Follow Up) the participant is called by the research staff to complete the pain questionnaire, document adverse events, and answer any study-related questions.

At Visit 5 (12 Week Follow Up) the participant will complete all the same assessments and questionnaires as baseline. All participants will return OrthoFeet shoes by this point.

Section G: Sample Size/Data Analysis

G1. Sample Size

How many subjects (or specimens, or charts) will be used in this study?

Local: 50 Worldwide: 50

Please indicate why you chose the sample size proposed:

This is a proof of concept study. The sample size is 50 eligible participating in a randomized crossover study. The sample size is convenient and is selected to detect a between group difference for the primary outcome (change in foot pain) with medium effect size (Cohen's $d=0.50$) with a dropout rate of 15%, alpha of 5%, and power of 80%. The anticipated effect size was estimated from our prior study (Najafi et al, Journal of Foot and Ankle Research, 2014) in which we observed a significant drop in foot pain after orthotic therapy compared to sham orthotics. Based on this pilot study, we will propose a Phase II study to validate the observed effect in the follow-up study.

G2. Data Analysis

Provide a description of your plan for data analysis. State the types of comparisons you plan (e.g. comparison of means, comparison of proportions, regressions, analysis of variance). Which is the PRIMARY comparison/analysis? How will the analyses proposed relate to the primary purposes of your study?

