Subjects may experience mild discomfort from the shoe. We will inform the subject to please notify the investigators if the shoe is uncomfortable.

Should the subject agree to the assessment involving the wearable sensor (PAMSys), the potential risks are considered minimal as well. This sensor will be used for assessing mobility performance and will perform physical tasks such as walking, sit-to-stand transitions, standing, physical activity monitoring etc. These assessments are non-invasive, safe, non-toxic, and non-ionizing as the other procedures described in this study. However, like any battery powered systems, there is a minimum risk of sensor malfunctioning. In addition, the study devices are not waterproof, and although they use a low powered battery (similar to a cellphone battery), in order to avoid any risk of shock the monitor should not be submerged or saturated with fluids during operations or cleaning. It does not emit any radiation to the human body, and does not offer any significant risk to the subject. The wearable sensors weigh less than .25 kg.

H2. Data and safety monitoring plan

Do the study activities impart greater than minimal risk to subjects?

No

H3. Coordination of information among sites for multi-site research

Is the BCM Principal Investigator acting as the SPONSOR-INVESTIGATOR for this multi-site research?

No or Not Applicable

Is BCM the COORDINATING CENTER for this multi-site research?

No or Not Applicable

Section I: Potential Benefits

Describe potential benefit(s) to be gained by the individual subject as a result of participating in the planned work.

Characterize the impact of OrthoFees on foot pain

Describe potential benefit(s) to society of the planned work.

Characterize the feasibility of the OrthoFees device on patient adherence, acceptability, user-friendliness, and perception of benefit for daily usage

Do anticipated benefits outweigh potential risks? Discuss the risk-to-benefit ratio.

This study brings no more than minimal risk to subjects as it only involves a non-invasive device. There are some risks associated with lack of comfort.

Section J: Consent Procedures

J1. Waiver of Consent

Will any portion of this research require a waiver of consent and authorization?

No

J1a. Waiver of requirement for written documentation of Consent

Will this research require a waiver of the requirement for written documentation of informed consent?

No

J2. Consent Procedures

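### Adverse events are scheduled for recording only at the Week 1 and Week 7 calls, so no scheduled query follows Group B's last five weeks in the shoes

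*Combined protocol and SAP*

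**What the plan says.** F1 sets five assessment times: "Participants will be assessed at baseline, week-1, week-6, week 7, and week 12". F2 gives the wearing periods: "Group A wears the OrthoFet shoes from baseline to 6 week follow up and Group B wears OrthoFet shoes from 6 week follow up" to Week 12. F1 puts 25 participants in each group.

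The visit descriptions in F2 differ in what they collect:

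- **Week 1 call (Visit 2):** "At Visit 2 (1 Week Follow Up) the participant is called by the research staff to complete the pain questionnaire, document adverse events".
- **Week 6 visit (Visit 3):** "At Visit 3 (6 Week Follow Up) the participant will complete all the same assessments and questionnaires as baseline". The groups switch at this visit.
- **Week 7 call (Visit 4):** staff telephone the participant to "complete the pain questionnaire, document adverse events, and answer any study-related questions".
- **Week 12 visit (Visit 5):** "At Visit 5 (12 Week Follow Up) the participant will complete all the same assessments and questionnaires as baseline".

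The baseline content in F2 covers the Foot Function Index, balance, gait, activity monitoring, quality of life, patient-reported scales, frailty, and a set of health questionnaires that includes fall history, foot examination and pain intensity. It names no adverse-event item.

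H1 adds one participant-initiated route: "We will inform the subject to please notify the investigators if the shoe is uncomfortable". H2 classes the study as no more than minimal risk and gives no monitoring plan. G2 gives no adverse-event analysis. No section states a look-back period for the calls or asks for onset dates.

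**The concern.** The two contacts that record adverse events each fall one week into a period. The two visits at the end of the periods, when six weeks of wear could be reviewed, do not name adverse events. Three consequences follow.

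- Group B's shoe period runs five weeks beyond the last scheduled query.
- Group A's shoe period is followed by a query only at Week 7, after a week without the shoes.
- If the Week 7 call looks back further than one week, its answers mix the two conditions: up to five on-shoe weeks and one off-shoe week for Group A, and up to five off-shoe weeks and one on-shoe week for Group B. Without onset dates, the events cannot be assigned to a condition.

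At stake is the trial's account of tolerability over six weeks of wear. H1 names mild discomfort from the shoe as a risk, and the study schedules adverse-event recording. As written, the schedule would not give a comparable on-shoe and off-shoe event record.

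**Working it through.** The plan states no coverage figure, so there is none to reproduce. The check is how much planned shoe time falls inside an interval that a scheduled adverse-event query could reach.

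**Inputs from the documents.** 25 participants per group (F1). Shoe periods of weeks 0–6 for Group A and 6–12 for Group B (F2). Adverse-event queries at weeks 1 and 7 (F2).

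**Assumptions.** Full retention. The look-back at the Week 7 call is not given, so it is varied from L = 1 week to L = 6 weeks, the latter reaching back to the Week 1 call.

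**Denominator.** 25 x 6 + 25 x 6 = 300 on-shoe person-weeks.

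**Group B.** The Week 1 call falls before its shoe period. The Week 7 call can reach only the first week of wear, whatever L is. Covered: 25 x 1 = 25 of 150. Uncovered: 25 x 5 = 125, which is 125/150 = 83% of Group B's shoe time and 125/300 = 42% of all shoe time. This part does not depend on L.

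**Group A.** The Week 1 call covers one week. The Week 7 call covers the off-shoe week 6–7 and then L − 1 on-shoe weeks. Covered: 1 + (L − 1) = L of 6 weeks.

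**Total.** Covered = 25 x (L + 1). Uncovered share = 1 − (L + 1)/12.

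| Look-back at Week 7 | Group A weeks covered | Group B weeks covered | Covered person-weeks | Uncovered |
|---|---|---|---|---|
| To the Week 1 call (L = 6) | 6 of 6 | 1 of 6 | 175 of 300 | 41.7% |
| 4 weeks | 4 of 6 | 1 of 6 | 125 of 300 | 58.3% |
| 2 weeks | 2 of 6 | 1 of 6 | 75 of 300 | 75.0% |
| 1 week, or since the Week 6 visit | 1 of 6 | 1 of 6 | 50 of 300 | 83.3% |

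The uncovered share is exactly half at L = 5 (1 − 6/12) and exceeds half only for a shorter look-back.

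**Balance between groups.** For any look-back longer than one week, Group A's shoe period is better covered than Group B's, by as much as 6 weeks to 1. With a one-week look-back the groups are equal, at one week in six each, and the Week 7 answers are not mixed. The cost is then the largest loss of coverage.

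**After the change.** Queries at weeks 1, 6, 7 and 12, each reaching back to the previous one, span weeks 0–12 without a gap: 300 of 300 person-weeks, with 6 of 6 weeks in both groups.

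**The case against.** The strongest reply is that Group B's last five weeks are not unobserved. The Week 12 visit repeats foot examination, fall history and pain measures, and the Foot Function Index is scheduled there too. These bear on the harms that footwear could plausibly cause. H1 sets no time limit on reporting discomfort. This stands: a reader might infer that those weeks are never covered, and the documents do not support that. What is missing is a scheduled adverse-event query. The repeated measures are not described as adverse-event collection and carry no onset date or recording rule, and the invitation to report concerns only an uncomfortable shoe.

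A reader might also infer that most shoe time lacks adverse-event collection. That requires a look-back shorter than five weeks, which the documents do not give. With a look-back to the Week 1 call the share is 42%.

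It could be argued that F2's general statement, that every visit has the same assessments and questionnaires, brings adverse events into Weeks 6 and 12. It does not, because it points to a list without an adverse-event item, and it conflicts with the two short calls. It should be reconciled with the visit descriptions.

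Two further replies stand. The calls fall in each group's first week of wear, which would be well timed if discomfort arises early, though the documents give nothing on timing. The consent form is not available here, so further reporting instructions in it cannot be excluded.

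**Conclusion.** The point holds as a minor gap in the visit schedule. Whatever the look-back, no scheduled adverse-event query follows 125 of 300 planned on-shoe person-weeks (42%), all in Group B. The total without a scheduled query lies between 42% and 83%, depending on a look-back that the plan leaves open. If the look-back exceeds one week, the two shoe periods are unequally ascertained, and events reported at Week 7 cannot be placed on or off the shoes without onset dates. The figures assume full retention and 25 per group.

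The documents do not support wider conclusions. The primary pain outcome is collected at all five times and is not affected. A reader might think that acceptability rests on one week of wear, but F2 places that survey at the end of six weeks of active use. Minimal risk is a prospective classification in Sections E1 and H2, not a finding the trial sets out to establish. The documents give no event rate, so the number of events that would be missed cannot be estimated.

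**What to change.** In F2:

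- Add to Visit 3, before the shoe switch, and to Visit 5: *document adverse events since the last adverse-event contact, with onset date*.
- Use the same wording at Visits 2 and 4, so that the look-back is fixed and the intervals join.
- Reconcile F2's general statement about identical content at every visit with the individual visit descriptions.

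In G2, state that adverse events will be reported by whether the participant was on or off the shoes at onset.

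The cost is one question at two in-person visits that already take place, an onset-date field in REDCap, and a few minutes per visit. The reported event count may be higher as a result.

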Other outcomes include gait parameters (e.g., gait speed, gait steadiness, gait variability, double stance, and limp assessed using a validated wearable gait analyzer), static balance (assessed using a validated wearable balance assessment system), acceptability and perception of benefit (assessed by technology acceptance model), adherence (daily duration of wearing orthofeet), physiological stress response (e.g., heart rate variability, HRV, rest heart rate, HR-rest assessed by a wrist worn sensor), community engagement (life space assessed by a questionnaire). Standard questionnaires and assessments will be performed to evaluate subjects' perception of benefit, user-friendliness, satisfaction, adherence, pain, sleep quality, concerns for fall, frailty, moving ability, risk of falling, anxiety, and quality of life.

Resources available to conduct the Human Research

The PI is a Professor of Surgery at the Baylor College of Medicine and has been involved in multiple clinical trials along with numerous publications in the area of outcomes evaluation, foot care, pain management, physical activity monitoring, gait and balance assessments in relation to diseases such as diabetes, cancer, plantar fasciitis, and aging population. Other team members include biomedical engineers/research scientists and study coordinators who are well acquainted with the study site, culture, and society. The wearable sensor technology is available at our center (iCAMP) for this study and includes LegSys (to assess Spatio-temporal parameters of gait), BalanSens (to assess postural control) and PAMSys (to monitor daily physical activity pattern and behavior), and Garmin (to assess daily physical activities and physiological stress response). All persons assisting with the study have received appropriate training and are extremely knowledgeable in their study-related duties and functions.

Inclusion Criteria:

50 total subjects will be recruited. Those eligible will meet the following inclusion criteria: Male or female 50 years or older Self-reported foot pain including heel, arch, or ball of foot pain

Exclusion Criteria:

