We will utilize REDCap, a HIPAA compliant database application, to ensure uniformity of data entry. A qualified postdoc will provide ongoing oversight and reporting of data quality, including missing data, timeliness of data entry, responsiveness to data queries, etc. Data meetings will be held twice monthly, and specific challenges will be addressed. Baseline descriptive statistics among randomized groups will include demographic and clinical variables, summarized as mean (SD) (or median, IQR) for continuous variables and frequency (percent) for categorical variables. For each baseline variable, the magnitude of group differences will be summarized as pairwise standardized mean/proportion differences (group difference divided by SD). Distributions of continuous trial outcomes will be evaluated for normality; normalizing transformations will be completed if needed. Group comparisons on primary outcomes will be by intent to treat. Statistical testing on the outcomes will be evaluated at alpha=0.05 each. Group comparisons on secondary and exploratory outcomes will control for multiple comparisons (false discovery rate) using the Benjamini-Hochberg method. In all models, outcomes will be summarized as mean group levels (with 95% CI) and mean group differences (with 95% CI). Results of the user experience questionnaires will be calculated as median (range) for each Likert-scale question. Unpaired t-tests, Mann-Whitney u-tests, and Chi-square will be used for baseline between groups comparison to verify effectiveness of randomization. To evaluate the effect of gender as biological variable, we will examine whether acceptability and benefits of footwear (between groups as well as compared to baseline) are different between men and women.

Section H: Potential Risks/Discomforts

H1. Potential Risks/Discomforts

Describe and assess any potential risks/discomforts; (physical, psychological, social, legal, or other) and assess the likelihood and seriousness of such risks:

The risk to participants of this study is considered to be minimal in a controlled environment with an attendant present. This research routine will not place subjects at higher risk than normal activities of daily living, and no more risk of harm or discomfort is associated with these tests than the discomfort normally incurred while performing normal activities.

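### No step collects Group A's shoes at Week 6, so the plan lets Group A hold them through its no-shoe period, and any continued wear would shrink the Weeks 6–12 and combined crossover contrasts

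*Combined protocol and SAP*

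**What the plan says.** Section F1 describes a randomized crossover of 50 people, 25 per group, with a switch at six weeks. Section F2 gives the steps:

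- **Visit 3 (Week 6):** "Group A will stop wearing OrthoFet shoes and continue the study without them". This instruction concerns wear; no hand-in is mentioned.
- **Visit 4 (Week 7):** "At Visit 4 (7 Week Follow Up) the participant is called by the research staff to complete the pain questionnaire, document adverse events", and to answer questions. Wear is not listed.
- **Visit 5 (Week 12):** "All participants will return OrthoFeet shoes by this point". This is the only statement on returning the shoes.

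The F1 design paragraph does not help, because its sentence on the period without shoes names the wrong group: "Group B will follow-up for six weeks without Orthofeet shoes". Group B has just been given them.

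On wear, F1 lists "adherence (daily duration of wearing orthofeet") among the other outcomes, and its next sentence puts adherence among the things that standard questionnaires and assessments will evaluate. No instrument is named. F2 adds that "All the same assessments and questionnaires are completed at each visit for all participants". Acceptability, by contrast, is tied to the active period: "assessed at the end of week 6 active use of OrthoFet (6- week for Group A and 12 week for group B").

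Section G2 says "Group comparisons on primary outcomes will be by intent to treat" and has no rule for shoes worn in the off period.

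**The concern.** In a crossover, Group A's Weeks 6–12 are its control period. A participant who still has the shoes, has foot pain and found the shoes helpful has a reason to keep wearing them. Intention to treat, rightly, still counts that time as without shoes, so the contrast shrinks if the shoes work. The risk runs one way: Group B has no study shoes before Week 6, so nothing offsets it.

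Interpretation also suffers. Continued wear and a benefit that outlasts wear would look the same in the pain scores, since Group A's pain stays low after Week 6 in both cases. Section G1 says the results will lead to a Phase II proposal, and the two explanations point to different designs. Without a return date or a wear record for that period, they would be hard to separate.

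**Working it through.** **The plan's own figure.** G1 gives N = 50 for d = 0.50, 15% dropout, alpha 5% and power 80%, and calls the size convenient. I could not reproduce 50 from these inputs. A paired t calculation with d in SDs of the within-person difference needs 34, and 34/0.85 = 40. A two-sided parallel comparison needs 63 per arm (normal approximation), 126 in all, and 126/0.85 = 148.2, so 149. The point here does not depend on this.

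**Inputs.** From the documents: 50 participants, 1:1, d = 0.50, 15% dropout, alpha 5%. Completers: 50 × 0.85 = 42.5, taken as 42 (21 per group). Assumed, because the documents are silent:

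- a fraction f of Group A continues to wear the shoes, unrelated to response and with full benefit at Week 12;
- the estimator is the equally weighted mean of the two groups' shoe-minus-no-shoe differences;
- testing is two-sided;
- d = 0.50 is in SDs of the within-person difference.

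**Effect on the contrasts.**

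- Baseline to Week 6: d, unchanged.
- Weeks 6–12, between groups: d(1 − f).
- Combined: Group A contributes d(1 − f) and Group B contributes d, so the mean is d(1 − f/2). The share lost is f/2, whatever the SD or correlation, as long as wear is unrelated to response.

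**Power of the combined estimate.** SE = 1/√42 = 0.154, 40 df, noncentral t:

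| f (assumed) | Weeks 6–12 contrast | Combined contrast | Share of combined lost | Power |
|---|---|---|---|---|
| 0 | 0.50 | 0.50 | 0 | 0.885 |
| 10% | 0.45 | 0.475 | 5% | 0.852 |
| 25% | 0.375 | 0.4375 | 12.5% | 0.790 |
| 50% | 0.25 | 0.375 | 25% | 0.660 |

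On this reading power is 0.816 with 4 of 21 Group A completers continuing and 0.795 with 5 of 21.

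**If d is in between-person SDs.** The effect in difference SDs is 0.50/√(2(1 − ρ)). At an assumed ρ = 0.3 it is 0.423, and power goes from 0.762 at f = 0 to 0.647 at f = 25%. At ρ = 0.7 it is 0.645, and power goes from 0.983 to 0.946.

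**If strong responders are the ones who continue.** Suppose half the sample has effect 1.0 and half has 0, and a quarter of Group A, all strong responders, continue. Group A then contributes 0.50 − 0.25 × 1.0 = 0.25, and the mean is (0.25 + 0.50)/2 = 0.375. That is a 25% loss, twice f/2, with power 0.660 if the difference SD is kept at 1.

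**The case against.** The strongest reply is that the intended exposure is clear. F2 limits Group A's wear to baseline through Week 6, the instruction to stop is given at a full assessment visit, and the Week 12 sentence can be read as a summary: Group A has already returned its shoes and Group B now does so. The F1 sentence naming Group B is a slip, not evidence that Group A keeps anything. Consent pages are not part of what was available and might cover return. All of this lowers the risk. It does not remove it, because an instruction to stop is not a collection and the stated rule allows return as late as Week 12.

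Three stronger readings are tempting, and the documents do not support them.

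- *Wear goes unchecked.* Adherence is to be evaluated by questionnaires, and assessments are said to repeat for all participants, so a wear question may well recur at Week 12. The gap is narrower: no named instrument, no stated coverage of Group A's off period, and no analysis rule.
- *The primary pain result is compromised.* G1 and G2 speak of between-group comparisons and name no primary time point or crossover estimator. If the primary comparison is between groups at Week 6, off-period wear does not touch it.
- *The trial falls below 80% power.* That threshold has meaning only on the within-person reading of d. As a parallel comparison with 21 per group, power at d = 0.50 is about 0.35 before any off-period wear.

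**Conclusion.** The point holds in a limited form. The plan permits Group A to hold the shoes in Weeks 6–12 and does not state that wear in that period will be recorded. If the shoes work and some of Group A continue, the bias in the Weeks 6–12 contrast and in any combined crossover contrast is toward zero.

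The documents give no wear rate, so the size is unknown. On the assumptions above, the combined estimate loses 5% to 25% of the effect for f between 10% and 50%, and more under selective wear. If the shoes are in practice collected at Week 6 and nobody wears them afterwards, the loss is zero. The power figures are scenarios, not predictions. I rate this a cheap improvement worth making, not a flaw that invalidates the design.

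**What to change.** 1. In F2, Visit 3, state that Group A returns the shoes at that visit and that the date of return is recorded.
2. In F2, Visit 5, limit the Week 12 return to Group B and any late returns from Group A.
3. Name the adherence question and ask it of both groups, in the same words, at the Week 7 call and the Week 12 visit. For example: on how many of the past 7 days were study shoes worn, and what footwear was mainly worn.
4. In G2, keep the intention-to-treat comparison as it is and report Group A's off-period wear beside it.
5. Correct the group named in the F1 sentence on the period without shoes.

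The cost is a small wording amendment, one added step for 25 participants at an existing visit, and about 50 × 2 × 1 minute = 100 minutes of questions over the whole study. Some Group A participants may be slightly less willing to stay in the study once the shoes are handed back. If collection at Week 6 is already the practice, the amendment only records it.
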